5.2 Definition of Dose-Limiting Toxicity

Determination of dose-limiting toxicity (DLT) will be based on toxicities observed in the first cycle of therapy and felt to be at least possibly related to study drug. A greater than 2-week delay for AEs before cycle 2 would be considered a DLT.

This study will follow design 3 of the Simon accelerated titration designs (Simon et al., 1997). We will accrue to the next dose level only after we have established safety at lower dose levels.

During this accelerated phase, there will be one patient per dose level. After the first instance of a drug-related Grade 2 toxicity (during the first cycle) at any dose level, the accelerated phase will end, and dose escalation will be changed to a 3 + 3 design. All decisions on dose expansion and DLT will be made on the first cycle of treatment.

When the accelerated phase ends, the trial will go back to a traditional 3+3 design. That is, additional patients will be placed on the dose level at which the last new patient was treated; 3 patients will be treated initially at each new dose level.

Number of Patients with DLT at a Given Dose Level	3+3 Escalation Decision Rule
0 out of 3	Enter 3 patients at the next dose level.
≥ 2	Dose escalation will be stopped. This dose level will be declared the maximally administered dose (highest dose administered). Three (3) additional patients will be entered at the next lowest dose level if only 3 patients were treated previously at that dose.
1 out of 3	Enter at least 3 more patients at this dose level. 
• If 0 of these 3 patients experience DLT, proceed to the next dose level.• If 1 or more of this group suffer DLT, then dose escalation is stopped, and this dose is declared the maximally administered dose. Three (3) additional patients will be entered at the next lowest dose level if only 3 patients were treated previously at that dose.
≤ 1 out of 6 at highest dose level below the maximally administered dose	This is generally the recommended phase 2 dose. At least 6 patients must be entered at the recommended phase 2 dose.

If ≥ 2 patients experience DLT on dose level -1, the study will be placed on hold and all data reviewed to make a decision about further evaluation of the study drug.

DLT is defined as an adverse event that is related (possibly, probably, or definitely) to

administration of study drug and fulfills one of the following criteria:

- 5.2.1 Inability to administer $\geq 75\%$ of doses of study drug in the absence of toxicity unless due to patient non-compliance.
- 5.2.2 Any treatment-related death
- 5.2.3 All \geq Grade 3 toxicities, with the exceptions noted below.

The following toxicities are NOT considered as DLTs:

- 5.2.4 Alopecia
- 5.2.5 Grade 3 fatigue, asthenia, anorexia, or constipation
- 5.2.6 Grade 3 nausea, vomiting, or diarrhea not requiring hospitalization, tube feeding, total parenteral nutrition, or prolonged hospitalization
- 5.2.7 Grade 3 alkaline phosphatase (ALP) or lactate dehydrogenase (LDH)
- 5.2.8 Grade 3 bilirubin elevation that is asymptomatic, returns to \leq Grade 2 levels in ≤ 7 days, and is not related to liver pathology (i.e., predominantly indirect bilirubin, Gilbert's syndrome)
- 5.2.9 Grade 3 electrolyte abnormality that improves to \leq Grade 1 after 48 hours with appropriate management.
- 5.2.10 Any degree of leukopenia or lymphopenia (except when associated with grade 4 neutropenia that lasts > 5 days) will not be considered dose limiting
- 5.2.11 Grade 3 or 4 neutropenia or thrombocytopenia lasting < 5 days

Aspartate aminotransferase (AST) or alanine aminotransferase (ALT) $\geq 3 \times$ upper limit of normal (ULN) with total bilirubin $\geq 2 \times$ ULN, alkaline phosphatase $< 2 \times$ ULN (FDA "Hy's Law") would be considered a DLT when determined to be related to study drug. Any other toxicity considered relevant by the investigator may be considered a DLT after discussion with CTEP.

Intra-patient dose escalation will be permitted if: **a**) there is no toxicity $>$ Grade 1 that is related (possibly, probably, or definitely) to the study drug at the initial dose level experienced by that patient, **b**) higher doses have been evaluated and completed without DLT, and **c**) the patient's disease is either stable or has progressed. Doses may be escalated, provided conditions a-c are met, up to the last evaluated dose level NOT associated with DLT.

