5.8 Dosing delays

Doses of CB-5339 will be held or modified only for adverse events that are felt to be at least possibly related to study drug. Treatment may be delayed for a maximum of 2 weeks for resolution of toxicities; in case toxicities do not resolve as defined below, the patient will not receive further therapy on this protocol and will be followed for resolution of toxicities. Dose modifications are intended for within-cycle and start of next cycle changes. If administration of CB-5339 is interrupted for any reason, it will not be made up, and counting of the cycle days will continue.

Patients will be allowed up to 2 dose reductions. For patients on dose level 1, the dose will be reduced to dose level -1 (25 mg/day; 3 days on/4 days off each week q 28-day cycles). Patients

who require a dose reduction will not have the dose re-escalated.

Treatment may be delayed for a maximum of 1 day during a cycle due to unavoidable scheduling conflicts.

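### Criterion 5.2.1 excludes toxicity while the DLT definition requires it, so dose loss from sub-Grade-3 visual toxicity has no reliable DLT rule

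*Combined protocol and SAP*

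**What the plan says.** The lead-in to the list in Section 5.2 reads: "DLT is defined as an adverse event that is related (possibly, probably, or definitely) to" administration of study drug, and the event must also meet a listed criterion. There are three. Criterion 5.2.1 is inability to give at least 75% "of doses of study drug in the absence of toxicity unless due to patient non-compliance". Criterion 5.2.2 is treatment-related death. Criterion 5.2.3 is any toxicity of Grade 3 or higher, subject to the exemptions in 5.2.4 to 5.2.11. Those exemptions include "Grade 3 fatigue, asthenia, anorexia, or constipation" and "Grade 3 or 4 neutropenia or thrombocytopenia lasting" less than 5 days.

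Two further provisions stand outside the list. Section 5.2 states: "A greater than 2-week delay for AEs before cycle 2 would be considered a DLT". It also allows: "Any other toxicity considered relevant by the investigator may be considered a DLT after discussion with CTEP".

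The dosing rules matter here too. Section 5.8 says: "Doses of CB-5339 will be held or modified only for adverse events that are felt to be at least possibly related to study drug". It also says: "Treatment may be delayed for a maximum of 2 weeks for resolution of toxicities". Interrupted doses are not made up, and cycle days keep counting. Under 5.9.1, ocular toxicity is the only Grade 2 toxicity for which treatment is interrupted. Section 5.10.1 sets no grade threshold for visual symptoms. Drug may be stopped until they resolve, restart is at the next lower level with CTEP medical monitor approval, and a patient whose symptoms have not resolved after 7 days should come off treatment.

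**The concern.** A dose-loss criterion normally catches toxicity that is not severe by grade but makes the dose undeliverable. Here the lead-in demands a drug-related adverse event, while the criterion's own qualifier appears to exclude toxicity. The carve-out for non-compliance suggests that drug-caused dose loss was what the authors meant, but the text does not say so. Two teams could classify the same patient differently.

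The case that matters most is visual toxicity below Grade 3. It was a visual effect that halted the predecessor compound (Section 2.2.5). It is also the one toxicity that this protocol interrupts at Grade 2, and it can end a patient's treatment at any grade.

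DLT counts drive the 3+3 table in 5.2 and the MTD definition in 8.1, and the MTD caps the RP2D (2.3). Section 8.2 allows for some non-evaluable patients without defining DLT evaluability. Section 11.1.1 makes everyone evaluable for toxicity from the first dose, which points to the patient staying in the denominator as a non-DLT. If the patient is set aside instead, the dose loss still goes uncounted.

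**Working it through.** There is no planned figure to reproduce, because the 75% limit is a rule. The check has two parts.

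**1. Which provisions reach the visual case?** Take a patient in the 3+3 stage with drug-related Grade 2 visual symptoms after the first dose, removed when they persist past 7 days.

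- 5.2.1: on its ordinary reading not met, because toxicity is present.
- 5.2.2 and 5.2.3: not met (no death, below Grade 3).
- Delay rule: it is framed as a delay of more than 2 weeks before cycle 2, and does not clearly reach someone taken off treatment after 7 days.
- Catch-all: permits a DLT call but does not require one.
- Accelerated phase: a first-cycle drug-related Grade 2 toxicity ends it. That does not make the patient a DLT in the 3+3 count.

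**2. What would a working 75% rule catch?**

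Inputs:

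- Schedule (5.1): 4 days on, 3 off, for 28 days. Dose days are 1–4, 8–11, 15–18 and 22–25, so 16 doses, and 0.75 × 16 = 12.
- Level -1 is 3 days on, 4 off: 12 doses, and 0.75 × 12 = 9.
- Held doses are lost (5.8).

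For a hold of L days starting on day s:

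doses given = 16 − (dose days from s to s + L − 1 that fall within days 1–28)

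The criterion is met if the result is below 12. Start days run from 2 to 28, because a drug-related hold cannot precede the first dose. All doses given count, at any level.

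| Hold (days) | Most doses lost | Start days that breach | Count of 27 |
|---|---|---|---|
| 7 | 4 | none | 0 |
| 8 | 5 | 2–4, 8–11, 15–18 | 11 |
| 9 | 6 | 2–4, 7–11, 14–18 | 13 |
| 10 | 7 | 2–4, 6–11, 13–18 | 15 |
| 11, 12, 13, 14 | 8 | 2–18 | 17 each |

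Total for 8–14 days: 11 + 13 + 15 + 4 × 17 = 107 of 7 × 27 = 189, or 57%.

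- Single 7-day hold: at least 16 − 4 = 12 doses, or 75%; no breach. At level -1, 12 − 3 = 9 of 12, also 75%; no breach.
- Two separate 7-day holds inside the cycle: 16 − 8 = 8, or 50%.
- Removal: last dose on day 1 gives 1/16 (6%); on day 17, 11/16 (69%); on day 18, 12/16 (75%). Removal therefore breaches when the last dose is on or before day 17.
- Level 1 patient restarting at level -1 after a 7-day hold: as few as 9 of 16 doses, partly because the new schedule has fewer dosing days. The fix needs a clause so that this schedule change does not itself create a DLT.

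**Effect on decisions.** One reclassified patient turns 0/3 (escalate) into 1/3 (add 3), or 1/6 (qualifies as MTD) into 2/6 (stop).

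As an illustration only, the chance of escalating past a dose is (1 − p)³ + 3p(1 − p)⁵, where p is the chance of a counted DLT. Assume p = 10% and that uncounted patients stay in as non-DLTs: 0.906. If a further 5%, 10% or 20% of patients had only an uncounted dose-loss event and these were counted, the figure would be 0.814, 0.709 or 0.494. All these rates are assumptions; none is in the documents.

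**The case against.** **The criterion can be parsed so that it works.** The no-toxicity phrase may modify the act of dosing: inability to give 75% of doses free of toxicity. It could also be read as applying even without Grade 3 toxicity. Either reading fits the lead-in and explains the non-compliance carve-out. This stands as far as it goes. A reader might infer that 5.2.1 can never be met, but that rests on one parse. The supportable claim is that the ordinary reading contradicts the lead-in and the text does not settle which reading governs.

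**Oversight already covers the gap.** Ocular events of Grade 3 or higher are DLTs under 5.2.3. Grade 2 ones end the accelerated phase. Restart at a lower level needs CTEP medical monitor approval. Section 12.1 requires Principal Investigator sign-off on dose decisions and calls with the CTEP Medical Officer at least monthly. These make discussion likely, and they narrow the problem. None of them says how the patient is to be counted.

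**The scenario may be uncommon.** Predecessor visual events had a median duration of 60 to 120 minutes (2.2.5), and CB-5339 is described as 10 times less potent on PDE6 (Figure 9). Removal for symptoms lasting beyond 7 days may well be unusual. This stands, and the predecessor's eye-disorder rates should not be used as a forecast.

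**Exempt events are exempt on purpose.** A reader might infer that every 8–14 day hold for Grade 3 fatigue or a short cytopenia is part of the same defect. The dose loss is real, since 5.9.2 to 5.9.4 hold drug until recovery and not for a fixed time. But 5.2.5 and 5.2.11 declare those events not dose-limiting, and a reworded 5.2.1 reaches them only if it overrides the exemptions.

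**The RP2D does not rest on DLTs alone.** Exposure and response also enter (2.3), and 15 expansion patients are monitored for DLT-type toxicity (5.3). This limits the consequence but leaves the escalation count unchanged.

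**Conclusion.** The point holds in a limited form and should be fixed. Criterion 5.2.1 conflicts with its lead-in on the ordinary reading, is ambiguous at best, and gives no reliable rule for cycle 1 dose loss caused by the drug. The case clearly left to discretion is visual toxicity below Grade 3 that leads to removal after 7 days or to repeated holds. Such a patient may have had as little as 1 of 16 doses and still meet no listed criterion.

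The size is one patient's classification at a time, which is enough to change a 3+3 decision. How often it would happen cannot be estimated from the documents. The 107 of 189 describes the calendar reach of a repaired criterion. A reader might infer from the table that long holds nearly always breach; they do not, because none starting after day 18 can.

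Assumptions: the delay rule is taken generously to cover holds over 14 days inside cycle 1, and all doses given count at any level. If the delay rule is read strictly as a delay to the start of cycle 2, the gap is wider.

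**What to change.** Replace 5.2.1 with:

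> Inability to administer at least 75% of planned cycle 1 doses (fewer than 12 of 16 given; fewer than 9 of 12 at level -1) because of drug-related toxicity. All doses given count, at any dose level. Doses removed only by a schedule reduction from level 1 to level -1 are not counted as missed.

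A dose reduction alone is then not a DLT. The sponsor should decide separately whether the criterion overrides 5.2.4 to 5.2.11, and should write the answer down. If the exemptions stay absolute, the rewording mainly reaches the ocular cases.

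The cost is one reworded criterion and no new data. The downside is that a few more patients may count as DLTs and some cohorts may expand to 6.

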Labs (CBC with differential; serum chemistries) will be performed at baseline (within 8 days of the start of protocol therapy), during weeks 1, 2, 3, and 4 of cycle 1, and at the start (+/- 1 day during the cycle and up to 3 days before start of a new cycle) and during week 1 of every cycle thereafter. For the first three patients enrolled on the study who will receive their initial week of treatment as inpatients, labs will also be performed on Cycle 1 Day 2 prior to CB-5339, on Day 3 based on the result from Day 2, on Day 4 prior to CB-5339, on Day 6 (Sunday at the Day Hospital), and on Day 8 (C1W2).

ECG will be performed at baseline (within 8 days of the start of protocol therapy) and will be

performed on day 1 pre-dose and at 2 hours post dose/the time to peak concentration of every subsequent cycle, and as clinically indicated.

Blood and urine samples for correlative PD and PK studies will be collected from all patients as described in [Section 7](#).

Paired tumor biopsies will be collected at baseline and then 4-6 hours after receiving the first dose in the expansion cohort; an optional biopsy may be collected at disease progression or “pre-progression” (defined as a 10-19% increase in tumor volume as shown on a restaging scan).

NEI associate investigators will perform an ophthalmology examination that includes optical coherence tomography (OCT), color vision testing, and a questionnaire on all patients during screening. The questionnaire will be repeated after treatment on cycle 1 day 1 or 2; the questionnaire and eye examinations can be repeated by NEI as clinically indicated. Details about the questionnaire and eye examinations can be found in [Appendix B](#) along with thresholds for pre-existing visual impairment. Patients should be encouraged to report any vision changes to the study team immediately.

CB-5339 is administered orally on a schedule of once daily, 4 days on and 3 days off (28-day cycle). Dose escalation will continue until the RP2D (MTD) is established. Intra-patient dose escalation will be permitted; refer to Section 5.2 regarding conditions for permitted intra-patient dose escalation.

Dose Escalation Schedule	
Dose level	Dose of CB-5339 (mg/day, once daily 4 days on/3 days off weekly)
-1	25 mg/day; 3 days on/4 days off
1 (starting)	25
2	50
3	100
4	150
5	225
6	300

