5.4 General Concomitant Medication and Supportive Care Guidelines

All patients will be provided with the best available supportive care. All concurrent medications should be documented prior to initiation of treatment and periodically reviewed with the patient.

It is not known which CYP enzymes are involved in the metabolism of CB-5339, and CB-5339 appears to be a potential inhibitor of **CYP2C19** and 2C9 in vitro. Therefore, for patients enrolled in the dose-escalation phase, avoid concomitant use of drugs that are strong inhibitors of CYP enzymes during the dose escalation phase, and substrates of CYP2C19 and 2C9 with narrow therapeutic indices, as this may affect the determination of the recommended phase 2 dose.

During the expansion phase, any concomitant use of CB-5339 and drugs that are strong inhibitors of CYP enzymes or substrates with narrow therapeutic indices for CYP2C19 (e.g., diazepam) or CYP2C9 (e.g., warfarin, phenytoin, many sulfonylureas (tolbutamide, glyburide, glibenclamide, glipizide, glimepiride) will be monitored closely. Consult <http://medicine.iupui.edu/flockhart/> for frequently updated information on drug interactions with cytochrome P450 isoenzymes.

Patients on study may be eligible for palliative radiotherapy to non-targeted lesions after completing 2 cycles of therapy at the Principal Investigator's discretion.

- 5.4.1 Nausea/Vomiting: Anti-emetics will not be administered routinely prior to CB-5339. However, if a patient develops nausea/vomiting, anti-emetics such as but not limited to prochlorperazine, metoclopramide, 5-HT3 antagonists, or aprepitant may be given. In addition, if a patient develops nausea and/or vomiting that is Grade 2 or greater, anti-emetics may be instituted prophylactically at the discretion of the investigator. Nausea and vomiting will be considered refractory if it does not resolve to grade 2 or less with a combination of at least 2 anti-emetics within 24 hours.

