5.9 Dose Modifications

- 5.9.1 Grade 2 drug-related toxicity: therapy will not be interrupted for Grade 2 toxicities with the exception of ocular toxicity.
- 5.9.2 Grade 3-4 drug-related non-hematologic toxicities: CB-5339 will be held until toxicities recover to \leq grade 1 or baseline (with the exception of alopecia) prior to re-initiating therapy at the next lower dose level. Electrolyte abnormalities will not require dose reduction if resolution to grade 1 or less is documented within 48 hours. Dose modifications for nausea, vomiting, and diarrhea will be made only if they are refractory to treatment (refer to Section 5.4). Diarrhea, nausea, and vomiting that fail to resolve to \leq Grade 2 within 24 hours despite adequate medical management are considered refractory.
- 5.9.3 Grade 3 hematologic toxicities: drug will be held for grade 3 hematologic toxicities, except leucopenia in the absence of neutropenia or lymphopenia, until resolution of toxicity to at least a grade 1 or baseline. Dose modification for grade 3 hematologic toxicity will be made only if the patient has recurrent grade 3 hematologic toxicity despite appropriate supportive care, e.g., growth factors; those experiencing recurrent grade 3 hematological toxicity despite optimal management may be dose reduced to the lower dose level.
- 5.9.4 Grade 4 drug-related hematologic toxicities of thrombocytopenia and neutropenia: CB-5339 will be held until toxicities recover to \leq grade 1 and therapy re-initiated at the next lower dose level. Agent will not be held or dose modified for leucopenia in the absence of neutropenia or lymphopenia.
- 5.9.5 All patients with grade 4 cardiac, respiratory, or neurologic toxicities at least possibly attributable to the investigational drug will be taken off treatment.

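### Intra-patient escalation is conditioned on toxicity at the starting dose only, so a patient with related Grade 2 toxicity at an already raised dose still qualifies for the next raise

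*Combined protocol and SAP*

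**What the plan says.** The last paragraph of Section 5.2 permits intra-patient escalation under three conditions:

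- (a) there has been no toxicity above Grade 1 related "to the study drug at the initial dose level experienced by that patient";
- (b) higher doses have been completed without a DLT;
- (c) the patient's tumor is stable or has progressed.

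The limit that follows is on dose, not on the number of raises: "Doses may be escalated, provided conditions a-c are met, up to the last evaluated dose level NOT associated with DLT". The treatment plan in Section 5 adds nothing: "Intra-patient dose escalation will be permitted; refer to Section 5.2 regarding conditions for permitted intra-patient dose escalation". Section 8.1 points back to 5.2 in the same way.

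Rules elsewhere that bear on a patient already at a raised dose:

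- Section 5.9.1, related Grade 2 events: "therapy will not be interrupted for Grade 2 toxicities with the exception of ocular toxicity".
- Section 5.9.2: "Dose modifications for nausea, vomiting, and diarrhea will be made only if they are refractory to treatment".
- Section 5.4.1: "Nausea and vomiting will be considered refractory if it does not resolve to grade 2 or less", allowing 24 hours and at least two anti-emetics.
- Section 5.8: patients "who require a dose reduction will not have the dose re-escalated".
- Section 5.2, accelerated phase: "After the first instance of a drug-related Grade 2 toxicity (during the first cycle) at any dose level, the accelerated phase will end".

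**The concern.** Condition (a) is the only one of the three that concerns the patient's own tolerance. Condition (b) is about other patients at higher levels, and (c) is about the tumor. Tying (a) to the starting dose is correct for a first raise, when the starting dose is also the current dose. At a second raise the two differ, and (a) looks back at a dose the patient has left.

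A patient who tolerated the starting dose, was raised, and then developed related Grade 2 toxicity would still satisfy (a), (b) and (c). Going higher in a patient who already has related toxicity above Grade 1 is what (a) prevents at the first raise, and nothing prevents it at the second. At stake is the safety of escalated patients in a first-in-human trial. The MTD is not at stake, because it rests on first-cycle DLTs.

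**Working it through.** The protocol gives no figure for this rule, so the check is to apply the wording step by step and see whether another section closes the gap.

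**1. Does another rule stop the raise?** Take a patient at a raised dose with related toxicity above Grade 1.

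| Event at the raised dose | Consequence (Sections 5.4, 5.9, 5.10) | Re-escalation barred by 5.8? |
|---|---|---|
| Grade 2, non-ocular | Treatment continues (5.9.1) | No |
| Nausea, vomiting or diarrhea settling to Grade 2 or less within 24 h on treatment | Not refractory, so no dose change (5.4.1, 5.4.2, 5.9.2) | No |
| Grade 3-4 electrolyte change resolved to Grade 1 or less within 48 h | No reduction (5.9.2) | No |
| First Grade 3 hematologic event | Held, reduced only if it recurs (5.9.3) | No |
| Other Grade 3-4 non-hematologic | Held, restarted one level lower (5.9.2) | Yes |
| Grade 4 neutropenia or thrombocytopenia | Held, restarted one level lower (5.9.4) | Yes |
| Visual symptoms, where dosing resumes | One level lower (5.10) | Yes |

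The bar in 5.8 depends on a dose reduction having been required, so the first four rows fall outside it.

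**2. Does the accelerated-phase trigger catch it?** No. The trigger counts first-cycle events only. Under 8.1 a higher level opens only after the last patient at the current level has been observed for at least one cycle, so any patient being raised is already past cycle 1.

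**3. The literal rule on the dose table (Section 5: 25, 50, 100, 150, 225, 300 mg).** Assume a patient starting at level 1 and raised one level at a time, related non-ocular Grade 2 toxicity appearing first at the current level, and (b) and (c) met. The step ratio is the next dose divided by the current dose.

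| Step (mg) | Ratio | Allowed by (a) as written | Allowed if (a) covers current and earlier levels |
|---|---|---|---|
| 25 to 50 | 50/25 = 2.0 | No | No |
| 50 to 100 | 100/50 = 2.0 | Yes | No |
| 100 to 150 | 150/100 = 1.5 | Yes | No |
| 150 to 225 | 225/150 = 1.5 | Yes | No |
| 225 to 300 | 300/225 = 1.33 | Yes | No |

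As written, the rule blocks 1 of 5 steps and allows 4; reworded, it blocks all 5.

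**4. Other starting levels.** A second raise needs at least two levels above the start, so it is possible from levels 1 to 4 only. The smallest second raise multiplies the dose by 2.0 from level 1 (50 to 100 mg), 1.5 from level 2 (100 to 150), 1.5 from level 3 (150 to 225) and 1.33 from level 4 (225 to 300).

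**5. Could a second raise happen in practice?** Assume single-patient levels, no enrollment gaps, and a first patient at 25 mg. The 50 mg level completes after two 28-day cycles and the 100 mg level after three. That patient could then be raised to 50 mg at the start of cycle 3 and become eligible for 100 mg after 3 × 28 = 84 days. This is the earliest case; gaps or three-patient cohorts lengthen it. Section 2.2 reports that several patients on the predecessor compound stayed on study for more than 4 months, one for 11. A second raise is therefore feasible, but the documents do not support a frequency.

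**The case against.** The strongest objection is that the text also fits a single raise. It tests the starting dose and then sets a ceiling, which could describe one move from start to ceiling. Alternatively, the initial level could mean the level held before whichever raise is being considered, with all three conditions rechecked each time. On either reading there is no gap. No section describes repeated raises, and the optional PK sampling after a dose adjustment (7.1) is compatible with one raise. This stands as a possible intention, but the protocol states neither reading, and a safety condition should not depend on an unstated one.

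Second, the accelerated-phase trigger is a weak comparator: it changes cohort size for the whole trial and does not stop escalation. That is fair. It shows that the protocol regards related Grade 2 toxicity as a signal for caution, but the concern does not rest on it.

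Third, the affected group is narrow. A patient must start at levels 1 to 4, tolerate the start, be raised, develop toxicity that forces no reduction, remain on treatment (5.5 lists progression as a reason to stop), and be raised again by an investigator who knows of the toxicity. This stands and limits the size of the problem.

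Fourth, there are real controls. Escalation is permitted rather than required, the target dose must be free of DLT, dose-escalation decisions need principal investigator sign-off with at least monthly calls with the CTEP Medical Officer(s) (12.1), and patients are examined at every cycle start. These reduce the risk, but none is a tolerance criterion at the current dose. The DLT-free ceiling can rest on a single other patient during the accelerated phase.

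**Conclusion.** The concern holds, conditional on a patient being raised more than once, which the protocol neither provides for nor excludes. In that event related toxicity above Grade 1 at the current dose, mainly non-ocular Grade 2 plus a few manageable Grade 3-4 events, does not bar the next raise. The four-of-five count assumes one-level moves from 25 mg with the other two conditions met throughout; the ratios describe dose exposure and do not measure harm. The change should be made on safety grounds; no trial conclusion depends on it. Confidence is medium, because the intended number of raises is not stated.

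**What to change.** Reword condition (a) in Section 5.2 along these lines: *no related toxicity above Grade 1 at the patient's current dose level or at any dose level previously received*. Alternatively, state that each patient may be raised only once, in which case the present anchor is correct. The rewording is the better choice: it does no harm if one raise was intended, and it keeps later levels open to patients who started low and are tolerating treatment.

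The cost is a few words in an amendment. The history and physical examination at each cycle start and the ongoing adverse event evaluation already supply the information, so no visits or tests are added.
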